6.4 Ipilimumab and Nivolumab

Dose modifications for nivolumab in combination with ipilimumab by adverse event type are detailed in Table 6.1. No dose reductions are allowed. General considerations for holding the dose(s) are as follows.

For the initial induction period, patients with Grade 2 or 3 events requiring discontinuation of treatment with the combination may consider continuing treatment with single agent nivolumab when the event resolves to grade 0-1 (or baseline, when baseline grade is >1). If induction cycles (Ipilimumab + Nivolumab) are held, they will be omitted, not delayed.

Nivolumab monotherapy may be continued at treating investigator discretion if there is evidence of clinical benefit. In this event, patient will continue nivolumab until AE is resolved and ipilimumab may be re-started or if ipilimumab is permanently discontinued (in congruence with guidelines in table below), then patient will continue nivolumab alone until cycles are completed. At completion of 4 dose of combination IPI + NIVO, patient may continue on nivolumab alone, as per protocol. If ipilimumab is permanently discontinued prior to receipt of 4 doses, nivolumab dosing should remain at the induction dosing (refer to Section 5) until completion of induction, and should then switch to maintenance dosing (refer to Section 5).

Example: Following IPI + NIVO treatment on Day 22, there is a grade 3 AE and Day 43 is held. The patient is treated with steroids and the grade 3 AE resolves quickly. The patient has been tapered down to a steroid dose of prednisone 5 mg po daily by Day 64 and the investigator wishes to continue protocol therapy with nivolumab monotherapy. The patient will receive nivolumab (induction dosing) on Day 64, and then continue as per the Study Calendar.

In addition to the AEs identified in the table below, ipilimumab and nivolumab dose should be delayed for any AE, laboratory abnormality or inter-current illness which, in the judgment of the treating investigator, warrants delaying the dose of study medication.

NOTE: Patients who receive systemic corticosteroids for any reason (including toxicity or management of symptoms brain metastases) must be off corticosteroids or have tapered down to an equivalent dose of prednisone 10 mg/day (dexamethasone \leq 1.5 mg PO daily) or less to continue immune checkpoint therapy.

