Maximum delay: The maximum amount of time that checkpoint inhibitor(s) can be held continuously is 12 weeks. If the patient cannot resume therapy within 12 weeks, the patient will

be removed from treatment with checkpoint inhibitor.

Patients requiring a delay of > 12 weeks due to ongoing immune-related toxicity or inability to taper prednisone to ≤ 10 mg PO daily (dexamethasone ≤ 1.5 mg PO daily) must go off checkpoint inhibitor therapy entirely.

Table 6.1 Dose Modification for Related Adverse Events

Treatment-related Adverse Event	Grade of Event	Nivolumab or Nivolumab/Ipilimumab
Nausea	\leq Grade 1	No dose modification
	Grade 2	Hold until \leq Grade 1 OR baseline (exceptions as noted below) ¹
	Grade 3	Off nivolumab and/or ipilimumab treatment (exceptions as noted below) ¹
	Grade 4	Off nivolumab and/or ipilimumab treatment
Recommended management: antiemetics.		
Diarrhea (immune-related enterocolitis)	\leq Grade 1	No dose modification
	Grade 2	Hold until \leq Grade 1 OR baseline
	Grade 3	Off nivolumab and/or ipilimumab treatment (exceptions as noted below) ¹
	Grade 4	Off nivolumab and/or ipilimumab treatment
Recommended management: Loperamide antidiarrheal therapy Dosage schedule: 4 mg at first onset, followed by 2 mg with each loose motion until diarrhea-free for 12 hours (maximum dosage: 16 mg/24 hours) Adjunct anti-diarrheal therapy is permitted and should be recorded when used. Please evaluate pituitary function prior to starting steroids if possible without compromising acute care. Evaluation for all patients for additional causes includes C. diff , acute and self-limited infectious and foodborne illness, ischemic bowel, diverticulitis, and IBD.		
Vomiting	\leq Grade 1	No dose modification
	Grade 2	Hold until \leq Grade 1 OR baseline (exceptions as noted below) ¹
	Grade 3	Off nivolumab and/or ipilimumab treatment (exceptions as noted below) ¹
	Grade 4	Off nivolumab and/or ipilimumab treatment
Recommended management: antiemetics.		
Other GI	\leq Grade 1	No dose modification
	Grade 2	Hold until \leq Grade 1 OR baseline (exceptions as noted below) ¹
	Grade 3	Off nivolumab and/or ipilimumab treatment (exceptions as noted below) ¹
	Grade 4	Off nivolumab and/or ipilimumab treatment
Patients with Grade 2 or 3 N-V should be evaluated for upper GI inflammation and other immune related events.		
Neurologic	\leq Grade 1	No dose modification

Treatment-related Adverse Event	Grade of Event	Nivolumab or Nivolumab/Ipilimumab

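### One clause in Section 6.4, read literally, lets nivolumab alone be given through an unresolved grade 2 event in induction; the rest of the protocol holds first and then resumes, so the clause should be reworded (minor).

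*Combined protocol and SAP*

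**What the plan says.** All of the text at issue concerns ipilimumab and nivolumab in induction. Section 6.4 opens by sending the reader to the table: "Dose modifications for nivolumab in combination with ipilimumab by adverse event type are detailed in Table 6.1". It then introduces its own paragraphs: "General considerations for holding the dose(s) are as follows".

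- **Paragraph 2.** After a grade 2 or 3 event that stops the combination, patients "may consider continuing treatment with single agent nivolumab when the event resolves to grade 0-1", or to baseline where baseline was above grade 1. Held induction cycles are omitted, not postponed.
- **Paragraph 3.** "Nivolumab monotherapy may be continued at treating investigator discretion if there is evidence of clinical benefit". It goes on: "patient will continue nivolumab until AE is resolved and ipilimumab may be re-started". An alternative branch covers permanent discontinuation of ipilimumab. The paragraph's only reference to the table sits in that branch.
- **Worked example.** After Day 22 dosing "there is a grade 3 AE and Day 43 is held". Nivolumab alone is given on Day 64, after the event has resolved and prednisone is down to 5 mg daily.
- **Steroid note.** Before checkpoint therapy continues, patients given systemic steroids "must be off corticosteroids or have tapered down to an equivalent dose of prednisone 10 mg/day" or less.
- **Table 6.1.** The action column is headed "Nivolumab or Nivolumab/Ipilimumab", so its holds apply to nivolumab alone as well as to the combination.

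**The concern.** Paragraph 3 makes nivolumab alone depend on investigator discretion and clinical benefit. It names no grade, and it lets dosing run up to the point of resolution. Paragraph 2 starts nivolumab alone only at grade 0-1 or baseline. An investigator who relies on paragraph 3 could therefore infuse nivolumab during a grade 2 event that the table says to hold for.

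At stake are patient safety and consistent dosing across sites. For hepatitis, the note in the liver row of Table 6.1 itself warns that continuing treatment can worsen active inflammation. Section 6.3 tells investigators which recommendation to follow when several conflict, but that rule is for troriluzole. Section 6.4 has no counterpart.

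**Working it through.** The plan gives no figure to reproduce. The check is a count of Table 6.1, a comparison of the text, and a count of dosing days.

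**1. Grade 2 actions in Table 6.1 (19 rows).**
- Hold until grade 1 or lower, or baseline where the row allows it: nausea, diarrhea, vomiting, other GI, neurologic, fever, skin, thrombocytopenia, neutropenia, renal, liver, amylase/lipase, all other events = 13.
- Hold on another condition: pneumonitis (pending evaluation), endocrine (until hormone replacement is stable), cardiac (suspected myocarditis; confirmed myocarditis goes off treatment) = 3.
- No hold: fatigue, any other laboratory abnormality = 2.
- Interrupt and resume the infusion: infusion reaction = 1.

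13 + 3 = 16 rows hold, and 16 + 2 + 1 = 19. Counting only holds to grade 1 or lower (or baseline) gives 13 of 19, which leads to the same conclusion.

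**2. Section 6.6 holds on both drugs.** It withholds for grade 2 hepatotoxicity, any neuropathy pending evaluation, enterocolitis pending evaluation, moderate to severe dermatitis, suspected endocrinopathy and symptomatic hypophysitis. Paragraph 3, read literally, cuts across all of these.

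**3. Text that shows the intended order.**
- Section 2.5 describes usual practice: therapy is interrupted, and nivolumab alone follows recovery and the end of steroids.
- Paragraph 2 of Section 6.4 and the Day 43/Day 64 example follow the same order of hold, then resume.
- The sentence after the example says both drugs should also be delayed, beyond the table's events, for anything the investigator judges to warrant it. That presupposes delay of both drugs for the table's events, and it uses discretion to add holds, not to lift them.

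**4. What the steroid note closes.** It stops dosing above 10 mg/day prednisone equivalent. The Section 6.6 dose for persistent enterocolitis is 0.5 mg/kg/day, and 0.5 × 20 kg = 10 mg/day, so any patient above 20 kg on that dose is blocked. Among the 13 rows, systemic steroids are named as a grade 2 option in 3 (enterocolitis, intracranial hemorrhage, skin events not improved within a week). That leaves 13 − 3 = 10 rows where the protocol directs none at grade 2. This counts rows, not patients. Section 5.5 permits steroids for any immune-related event, and Section 6.4 refers sites to an outside guideline for further management.

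**5. Doses at stake.** Induction doses fall on Days 1, 22, 43 and 64. Paragraph 3 requires evidence of clinical benefit. The Study Calendar schedules the first on-study brain MRI at Day 43 and the first body CT at Day 85. The realistic exposure is therefore Days 43 and 64: 2 doses × 1 mg/kg = 2 mg/kg. Day 22 would need an unscheduled scan or a purely clinical judgment of benefit; adding it gives an upper limit of 3 doses. For a patient above the steroid limit the difference is 0.

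**The case against.** The strongest case on the other side is that the document already settles the matter. The opening of Section 6.4 gives the detail to Table 6.1 and calls its own paragraphs general. Paragraph 3 speaks of continuing monotherapy, which most naturally means the monotherapy that paragraph 2 has just allowed at grade 0-1. A sequential reading then works: nivolumab alone from grade 1, and ipilimumab later. Section 2.5, the example and the sentence on additional delays all point the same way. Hepatitis, the clearest harm, is covered by a table row, a note in that row and an explicit Section 6.6 hold.

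Most of this stands, and it is why the point is minor. It does not remove the clause. Paragraph 2 uses resolution to mean reaching grade 0-1; with that meaning in paragraph 3, nivolumab is given until grade 0-1, that is, during grade 2. Nothing says that the table limits the discretion given there.

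A reader might infer more: that the protocol flatly contradicts itself, or that it authorizes dosing through toxicity. The surrounding text does not support that. Nor does the point carry over to grade 3 in general. Section 6.6 permanently stops both drugs for severe enterocolitis, grade 3-5 hepatotoxicity or pancreatitis, severe neuropathy and other severe immune-mediated reactions.

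**Conclusion.** The point holds as a drafting fault in one clause, of minor severity. Read literally, it permits nivolumab alone during an unresolved grade 2 event in induction, against paragraph 2, the example, 16 of 19 rows of Table 6.1 and the Section 6.6 holds. The intended order, hold then resume, is clear from the rest of the document.

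The realistic size is up to two 1 mg/kg nivolumab doses per affected patient. This assumes that evidence of benefit normally comes from a scheduled scan, that the event stays above grade 1 at those visits, and that steroids are at or below the limit. The documents do not allow the number of such patients to be derived.

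A reader might also infer a threat to the efficacy result. There is no basis for that: the same wording governs both arms of a double-blind randomization, and the primary endpoint is analyzed by intention to treat.

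**What to change.** Replace the clause in paragraph 3 with wording such as:

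*In this event, once the hold conditions in Table 6.1 and Section 6.6 are met (generally grade 0-1 or baseline, and prednisone equivalent at or below 10 mg/day), or where Table 6.1 requires no hold, the patient may receive nivolumab alone until ipilimumab may be re-started per Table 6.1 at a later scheduled induction visit.*

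The branch on permanent discontinuation of ipilimumab then follows unchanged.

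Two things should be left alone. Do not add a grade 0 requirement for restarting ipilimumab: the table generally releases its holds at grade 1 or lower, so this would be a new clinical threshold. Do not add a blanket statement that table holds override all discretion: the note on grade 2 intracranial hemorrhage is itself permissive about holding, and the row-specific notes should stay as they are.

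The cost is one reworded clause in the next amendment, with no added visits, data or patients.

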6.5 Treatment of Infusion Reactions Associated with Ipilimumab and/or Nivolumab

Since ipilimumab contains only human protein sequences, and since nivolumab is a fully human monoclonal antibody, it is less likely that any allergic reaction will be seen in patients receiving these agents. However, it is possible that infusion of ipilimumab or nivolumab will induce a cytokine release syndrome that could be evidenced by fever, chills, rigors, rash, pruritus, hypotension, hypertension, bronchospasm, or other symptoms. No prophylactic pre-medication

should be given unless indicated by previous experience in an individual patient. Reactions should be treated based upon the following recommendations.

- For mild symptoms (e.g., localized cutaneous reactions such as mild pruritus, flushing, rash):
 - Decrease the rate of infusion until recovery from symptoms, remain at bedside and monitor patient.
 - Complete the infusion at the initial planned rate.
 - Diphenhydramine 50 mg IV may be administered at the discretion of the treating physician and patients may receive additional doses with close monitoring.
 - Premedication with diphenhydramine may be given at the discretion of the investigator for subsequent doses.

- For moderate symptoms (any symptom not listed above [mild symptoms] or below [severe symptoms] such as generalized pruritus, flushing, rash, dyspnea, hypotension with systolic BP >80 mmHg):
 - Interrupt infusion of offending agent.
 - Administer diphenhydramine 50 mg IV.
 - Monitor patient closely until resolution of symptoms.
 - Corticosteroids may abrogate any beneficial immunologic effect, but may be administered at the discretion of the treating physician.
 - Resume infusion after recovery of symptoms.
 - At the discretion of the treating physician, infusion may be resumed at one half the initial infusion rate, then increased incrementally to the initial infusion rate.
 - If symptoms develop after resumption of the infusion, the infusion should be discontinued and no additional ipilimumab or nivolumab should be administered that day.
 - The next dose will be administered at its next scheduled time and may be given with pre-medication (diphenhydramine and acetaminophen) and careful monitoring, following the same treatment guidelines outlined above.
 - At the discretion of the treating physician additional oral or IV antihistamine may be administered prior to dosing.

- For severe symptoms (e.g., any reaction such as bronchospasm, generalized urticaria, systolic blood pressure < 80 mm Hg, or angioedema):
 - Immediately discontinue infusion and disconnect infusion tubing from the patient.
 - Consider bronchodilators, epinephrine 1 mg IV or subcutaneously, and/or diphenhydramine 50 mg IV, with solumedrol 100 mg IV, as needed.
 - Patients should be monitored until the investigator is comfortable that the symptoms will not recur.
 - No further ipilimumab (if related to ipilimumab) or nivolumab (if related to nivolumab) will be administered.

6.5 Treatment of Ipilimumab-Related Isolated Drug Fever

In the event of isolated drug fever, the investigator must use clinical judgment to determine if the

fever is related to the ipilimumab or to an infectious etiology. If a patient experiences isolated drug fever, for the next dose, pre-treatment with acetaminophen or non-steroidal anti-inflammatory agent (investigator discretion) should be instituted and a repeated antipyretic dose at 6 and 12 hours after ipilimumab infusion, should be administered. The infusion rate will remain unchanged for future doses. If a patient experiences recurrent isolated drug fever following premedication and post dosing with an appropriate antipyretic, the infusion rate for subsequent dosing should be decreased to 50% of the previous rate. If fever recurs following infusion rate change, the investigator should assess the patient's level of discomfort with the event and use clinical judgment to determine if the patient should receive further ipilimumab.

6.6 Monitoring and Management of Immune-mediated Adverse Reactions

Immune-mediated Enterocolitis

The clinical presentation of GI immune-related AEs included diarrhea, increase in the frequency of bowel movements, abdominal pain, or hematochezia, with or without fever. However, inflammation may occur in any part of the GI tract including esophagitis and gastritis. Fatalities due to GI perforation have been reported in clinical trials of ipilimumab. Patients should be carefully monitored for GI symptoms that may be indicative of immune-related colitis, diarrhea, or GI perforation. Diarrhea or colitis occurring after initiation of ipilimumab therapy should be evaluated to exclude infectious or alternate etiologies. In clinical trials, immune-related colitis was associated with evidence of mucosal inflammation, with or without ulcerations, and lymphocytic infiltration.

Monitor patients for signs and symptoms of enterocolitis (such as diarrhea, abdominal pain, mucus or blood in stool, with or without fever) and bowel perforation (such as peritoneal signs and ileus). In symptomatic patients, rule out infectious etiologies and consider endoscopic evaluation to establish etiology and for persistent or severe symptoms. *C.difficile* toxin has been detected in several patients with colitis and may be an independent entity or may co-exist with ipilimumab induced inflammatory colitis.

Withhold ipilimumab and/or nivolumab dosing for any patients with enterocolitis pending evaluation; administer anti-diarrheal treatment and, if persistent evaluate with colonoscopy and initiate systemic corticosteroids at a dose of 0.5 mg/kg/day prednisone or equivalent.

Permanently discontinue ipilimumab and nivolumab in patients with severe enterocolitis and initiate systemic corticosteroids at a dose of 1 to 2 mg/kg/day of prednisone or equivalent. Upon improvement to Grade 1 or less, initiate corticosteroid taper and continue to taper over at least one month. In clinical trials, rapid corticosteroid tapering has resulted in recurrence or worsening symptoms of enterocolitis in some patients.

Patients have been treated with anti-TNF agents for persistent colitis not responding to steroids.

Please note autoimmune pancreatitis may cause abdominal pain and should be included in all evaluations. Enteritis may occur occasionally with other autoimmune events including hepatitis, pancreatitis, and endocrine insufficiency, which should be evaluated as clinically indicated.

Immune-mediated Hepatitis and Pancreatitis

Hepatic immune-related AEs were mostly clinically silent and manifested as transaminase or bilirubin laboratory abnormalities. Fatal hepatic failure has been reported in clinical trials of ipilimumab. Serum transaminase and bilirubin must be evaluated before each dose of ipilimumab and nivolumab as early laboratory changes may be indicative of emerging immune-related hepatitis/ pancreatitis and elevations in liver function tests (LFTs) may develop in the absence of clinical symptoms. Increase in LFT or total bilirubin should be evaluated to exclude other causes of hepatic injury, including infections, disease progression, or other medications, and monitored until resolution. Liver biopsies from patients who had immune-related hepatotoxicity showed evidence of acute inflammation (neutrophils, lymphocytes, and macrophages).

Monitor liver function tests (hepatic transaminase and bilirubin levels) and assess patients for signs and symptoms of hepatotoxicity/ pancreatitis before each dose of ipilimumab and nivolumab. In patients with hepatotoxicity, rule out infectious or malignant causes and increase frequency of liver function test monitoring until resolution. Withhold ipilimumab and nivolumab in patients with Grade 2 hepatotoxicity.

Permanently discontinue ipilimumab and nivolumab in patients with Grade 3–5 hepatotoxicity/pancreatitis and administer systemic corticosteroids at a dose of 1 to 2 mg/kg/day of prednisone or equivalent. When liver function tests show sustained improvement or return to baseline, initiate corticosteroid tapering and continue to taper over 1 month. Across the clinical development program for ipilimumab, mycophenolate treatment has been administered in patients who have persistent severe hepatitis despite high-dose corticosteroids.

Immune-mediated Dermatitis

Skin immune-related AEs presented mostly frequently as a rash and/or pruritus. Some patients reported vitiligo associated with ipilimumab administration. Fatal toxic epidermal necrolysis has been reported in clinical trials of ipilimumab.

Monitor patients for signs and symptoms of dermatitis such as rash and pruritus. Unless an alternate etiology has been identified, signs or symptoms of dermatitis should be considered immune-mediated.

Permanently discontinue ipilimumab and nivolumab in patients with Stevens-Johnson syndrome, toxic epidermal necrolysis, or rash complicated by full thickness dermal ulceration, or necrotic, bullous, or hemorrhagic manifestations. Administer systemic corticosteroids at a dose of 1 to 2 mg/kg/day of prednisone or equivalent. When dermatitis is controlled, corticosteroid tapering should occur over a period of at least 1 month. Withhold ipilimumab and nivolumab dosing in patients with moderate to severe signs and symptoms.

For mild to moderate dermatitis, such as Grade 2 localized rash and pruritus, treat symptomatically. For persistent Grade 2, Grade 3, or greater, topical steroids may be administered. Administer topical or systemic corticosteroids as indicated if there is no improvement of symptoms within 1 week.

Immune-related Neurological Events

Fatal Guillain-Barré syndrome has been reported in clinical trials of ipilimumab. Patients may present with muscle weakness and myasthenia gravis, cranial nerve palsy (n VII Bell's palsy), and aseptic meningitis, encephalopathy. Unexplained motor neuropathy, muscle weakness, or sensory neuropathy lasting more than 4 calendar days should be evaluated and non-inflammatory causes such as disease progression, infections, metabolic syndromes, nerve entrapment, and medications should be excluded as causes.

Withhold ipilimumab and nivolumab dosing in patients with any evidence of neuropathy pending evaluation.

Monitor for symptoms of motor or sensory neuropathy such as unilateral or bilateral weakness, sensory alterations, or paresthesia. Permanently discontinue ipilimumab and nivolumab in patients with severe neuropathy (interfering with daily activities) such as Guillain-Barré-like syndromes. Institute medical intervention as appropriate for management of neuropathy and other neurologic events. Consider initiation of systemic corticosteroids at a dose of 1 to 2 mg/kg/day prednisone or equivalent for severe neuropathies.

Immune-mediated Endocrinopathies

Ipilimumab and/or nivolumab can cause inflammation of endocrine organs including thyroid (Hashimoto's thyroiditis with positive antibodies) and adrenal glands, hypophysitis, hypopituitarism, and resulting thyroid and adrenal insufficiency, low ADH, prolactin, FSH, LH. Hyperthyroid with Graves' disease and positive antibody has been reported. Patients may present with subtle and nonspecific symptoms. The most common clinical presentation includes headache and fatigue. Symptoms may also include visual field defects, behavioral changes, and electrolyte disturbances including hyponatremia and hypotension. Adrenal crisis as a cause of the patient's symptoms should be excluded. Based on the available data with known outcome, most of the patients symptomatically improved with hormone replacement therapy. Long term hormone replacement therapy with HC and Synthroid will typically be required for patients developing hypophysitis/hypopituitarism after treatment with ipilimumab alone or with nivolumab. Some patients have regained partial function following steroid treatment.

Monitor patients for clinical signs and symptoms of hypophysitis, adrenal insufficiency (including adrenal crisis), and hyper- or hypothyroidism. Headache is often the first symptoms of hypophysitis. Patients may present with fatigue, headache, mental status changes, loss of libido, abdominal pain, unusual bowel habits, and hypotension, or nonspecific symptoms which may resemble other causes such as brain metastasis or underlying disease. Unless an alternate etiology has been identified, signs or symptoms of endocrinopathies should be considered immune-mediated and drugs withheld pending evaluation. Patients may demonstrate both central (hypophysitis) and peripheral adrenal and thyroid insufficiency. Evaluation of hypophysitis should include pituitary MRI.

Endocrine evaluation, including TSH, should be performed at baseline prior to initial treatment. Monitor thyroid function tests and clinical chemistries at the start of treatment and hold blood for possible evaluation should clinical events require determining baseline function and anti-thyroid antibodies. In a limited number of patients, hypophysitis was diagnosed by imaging studies

through enlargement of the pituitary gland.

Withhold ipilimumab and nivolumab dosing in patients symptomatic for hypophysitis. Initiate systemic corticosteroids at a dose of 1 to 2 mg/kg/day of prednisone or equivalent and initiate appropriate hormone replacement therapy.

Other Immune-mediated Adverse Reactions, Including Ocular Manifestations

Ocular inflammation, manifested as Grade 2 or Grade 3 episcleritis or uveitis, was associated with concomitant diarrhea in a few patients (< 1%) and occasionally occurred in the absence of clinically apparent GI symptoms. Other presumed immune-related AEs reported include, but were not limited to, arthritis/arthralgias, pneumonitis, pancreatitis, autoimmune (aseptic) meningitis, autoimmune nephritis, pure red cell aplasia, noninfective myocarditis, polymyositis, and myasthenia gravis, of which were individually reported for < 1% of patients.

The following clinically significant immune-mediated adverse reactions were seen in less than 1% of ipilimumab-treated patients in Study 1: nephritis, pneumonitis, pulmonary granuloma resembling sarcoidosis, meningitis, pericarditis, uveitis, iritis, ITP, neutropenia and hemolytic anemia.

Across the clinical development program for ipilimumab, the following likely immune-mediated adverse reactions were also reported with less than 1% incidence: myocarditis, angiopathy, temporal arteritis, vasculitis, polymyalgia rheumatica, conjunctivitis, blepharitis, episcleritis, scleritis, leukocytoclastic vasculitis, erythema multiforme, psoriasis, pancreatitis, arthritis, and autoimmune thyroiditis.

Permanently discontinue ipilimumab and nivolumab for clinically significant or severe immune-mediated adverse reactions. Initiate systemic corticosteroids at a dose of 1 to 2 mg/kg/day prednisone or equivalent for severe immune-mediated adverse reactions.

Administer corticosteroid eye drops to patients who develop uveitis, iritis, or episcleritis. Permanently discontinue ipilimumab for immune-mediated ocular disease that is unresponsive to local immunosuppressive therapy.

Overall, immune-related AEs commonly started within 3 to 10 weeks from first dose, were successfully managed in most instances by omitting doses, discontinuing dosing, and/or through administering symptomatic or immunosuppressive therapy, including corticosteroids, as mentioned above. Immune-related AEs generally resolved within days to weeks in most patients.

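### After grade 3 immune hepatotoxicity in induction, Section 6.4 permits nivolumab alone on recovery while Section 6.6 stops both checkpoint inhibitors permanently, and no precedence is stated

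*Combined protocol and SAP*

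**What the plan says.** **Section 6.4** refers to Table 6.1 for modifications by event type and then gives general considerations. For induction, "patients with Grade 2 or 3 events requiring discontinuation of treatment with the combination may consider continuing treatment with single agent nivolumab" after resolution to grade 0-1, or to baseline where that was higher. No event type is excluded and Section 6.6 is not mentioned. The investigator may continue nivolumab alone where there is clinical benefit. The section also foresees ipilimumab being dropped on its own: "if ipilimumab is permanently discontinued (in congruence with guidelines in table below), then patient will continue nivolumab alone until cycles are completed". Its worked example is an unspecified grade 3 event after the Day 22 dose. The event is treated with steroids and followed by single-agent nivolumab on Day 64.

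**Section 6.6** gives instructions by organ. For the liver: "Permanently discontinue ipilimumab and nivolumab in patients with Grade 3–5 hepatotoxicity/pancreatitis". For the gut: "Permanently discontinue ipilimumab and nivolumab in patients with severe enterocolitis". It gives the same two-drug stop for severe neuropathy, described there as interfering with daily activities.

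**Table 6.1** has one action column for both drugs, headed "Nivolumab or Nivolumab/Ipilimumab". The grade 3 diarrhea/enterocolitis and neurologic cells read "Off nivolumab and/or ipilimumab treatment (exceptions as noted below" and carry footnote 1. The grade 3 liver cell has the same and/or wording without the exceptions pointer. Footnote 1 refers to Section 6.6 for treatment management.

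**The concern.** A patient with grade 3 immune hepatitis in induction who recovers is covered by two rules. One permits more nivolumab and the other forbids it. Two sites could each follow a section of the protocol and treat the same event in opposite ways.

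This is a safety matter. Section 6.6 itself notes deaths in ipilimumab trials from gastrointestinal perforation, hepatic failure and Guillain-Barré syndrome. The permissive route is also a likely one. Section 2.5 describes it as the general approach after significant induction toxicity: the remaining combination cycles are omitted and, on recovery and off steroids, nivolumab is given alone.

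**Working it through.** The protocol states no figure on this point, so the check is a comparison of texts followed by one count.

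**Step 1. The same event under each rule (grade 3, induction, recovered to grade 0-1).**

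| Event | Section 6.4 text | Table 6.1, grade 3 cell | Section 6.6 |
|---|---|---|---|
| Hepatotoxicity | Nivolumab alone permitted | Off, and/or; no footnote | Both stop permanently; grade 3-5 stated |
| Enterocolitis | Nivolumab alone permitted | Off, and/or; footnote 1 | Both stop permanently if severe |
| Neuropathy | Nivolumab alone permitted | Off, and/or; footnote 1 | Both stop permanently if severe |

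The first row needs no interpretation of grade. The other two need severe to mean grade 3, which Section 6.6 does not say.

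**Step 2. Does Table 6.1 settle it?** There are two readings.
- And/or leaves open which drug stops. The table is then silent on the question, and the 6.4 clause about stopping ipilimumab alone fits this reading.
- Given the column heading, and/or means whichever drugs the patient is receiving. The table then agrees with 6.6, and the 6.4 text conflicts with both.

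The conflict remains on either reading. Elsewhere the protocol is more exact: for severe infusion reactions it stops each drug according to which one caused the reaction.

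**Step 3. Is there a precedence rule?** There are three candidates.
- The 6.4 reference to the table below points to Table 6.1, not to 6.6.
- Footnote 1 points to 6.6 for management, does not say that 6.6 overrides 6.4, and is absent from the grade 3 liver cell.
- The conflict rule in Section 6.3 (take the lowest dose level) concerns troriluzole only.

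None decides between 6.4 and 6.6.

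**Step 4. Exposure at stake per patient.** By the study calendar and Section 5.3, maintenance nivolumab is given every 28 days from Day 85 to Day 337:

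(337 − 85) / 28 + 1 = 252 / 28 + 1 = 10 infusions.

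- Restart by Day 85: 10 under 6.4, 0 under 6.6.
- Restart on Day 113: 9 against 0.
- Restart on Day 141: 8 against 0.

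A Day 85 restart is within the 84-day limit on checkpoint inhibitor interruption even if the last infusion was on Day 1 (85 − 1 = 84). Prednisone must be at 10 mg/day or less. The counts assume no progression and no further toxicity.

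**Step 5. How many patients?** The rules cover everyone, up to 18 + 90 = 108. Section 2.5 gives grade 3-4 peripheral motor neuropathy at 1% in the earlier brain-metastasis study of this backbone; 0.01 × 108 is about 1 patient, if that rate carries over. No hepatitis or colitis rate is given. The 55% grade 3-4 toxicity in Section 2.5 covers all events and cannot stand in for one.

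**The case against.** The best defence is that 6.4 only permits, whereas 6.6 commands. A site that stops both drugs breaks nothing in 6.4, so both sections can be obeyed. Section 6.4 calls its text general, and a careful reader would let the specific rule prevail. The liver cell says off with no exception, and footnote 1 requires anyone at substantial clinical risk in the investigator's judgment to stop. The Day 64 example need not collide with 6.6 either, since its grade 3 event is unspecified and could be one for which 6.6 only withholds.

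Much of this stands. There is a compliant course, and the example alone proves nothing. But a site that uses the permission after grade 3 hepatitis breaks 6.6 while acting within 6.4 and in line with Section 2.5. Specific-over-general is a sensible inference that the protocol never states.

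A reader might infer that the conflict extends to grade 3 pneumonitis, renal and all other immune events, because 6.6 also says "Permanently discontinue ipilimumab and nivolumab for clinically significant or severe immune-mediated adverse reactions". The documents do not support a row-by-row contradiction there. That catch-all is loosely worded and the corresponding table cells already say off without exceptions. Section 6.6 also puts pneumonitis and nephritis below 1% of ipilimumab-treated patients.

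**Conclusion.** The inconsistency is real and should be corrected. It is explicit for grade 3 hepatotoxicity. It extends to enterocolitis and neuropathy if severe is read as grade 3. Its size per patient is up to 10 maintenance infusions against none, which is a best-case maximum and not an expected effect. The number of patients cannot be stated beyond the partial neuropathy figure.

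A reader might infer that 6.6 is the intended rule and 6.4 the mistake. The documents do not show that, and Section 2.5 points the other way. Nor should a reader infer bias between arms: both blinded arms receive the same backbone under the same rules, and no effect on the primary comparison is claimed.

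**What to change.** The sponsor should decide, for hepatotoxicity, enterocolitis and neuropathy separately, which rule governs, and make the sections agree.

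- **Option 1 (the safer default until decided).** Add to 6.4 that the single-agent nivolumab permission and the Day 64 example do not apply to events for which 6.6 requires both drugs to stop permanently.
- **Option 2.** Where rechallenge after recovery is intended, in line with Section 2.5, amend 6.6 for that event.

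Under either option, replace and/or in the grade 3 diarrhea/enterocolitis, liver and neurologic rows of Table 6.1 with an explicit entry for each drug. Keep intracranial hemorrhage as a separate entry in the neurologic row, because the 6.6 stop names neuropathy. Stating the grade that severe means in 6.6 would remove the remaining inference.

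The cost is a wording amendment and a memo to sites, with no added patients, visits or procedures. The downside of option 1 is that some patients who recover lose the chance of nivolumab rechallenge.
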